7.1 Discontinuation of Study Intervention

Withdrawal from study treatment period

Patients **MUST** be withdrawn from the study treatment combination if any of the following occurs:

- At their own request or at the request of their legally acceptable representative. At any time during the study and without giving reasons, a patient may decline to participate further. The patient will not suffer any disadvantage as a result.
- If, in the investigator's opinion, continuation of the study treatment would be harmful to the patient's well-being.
- Clinical progression as per iRECIST (every effort should be made to obtain radiological confirmation of disease progression [PD] during active FU). Note: In cases where radiographic evaluation is not possible, clinical progression may be used. Clinical progression is based on the judgment of the investigator (e.g., defined as worsening of the ECOG PS ≥ 3 or symptomatic deterioration including increase in liver function tests).
- The development of a second primary malignancy that requires a different treatment.
- Development of any intercurrent illness or situation which may, in the judgment of the investigator, affect assessments of clinical status and study endpoints to a relevant degree.

- Severe allergic reactions, such as exfoliate erythroderma, anaphylaxis, or vascular collapse.
- Start of subsequent systemic anti-cancer treatment
- Use of illicit drugs or other substances that may, in the opinion of the investigator or their designated associate(s), have a reasonable chance of contributing to toxicity or otherwise confound the results.
- Pregnancy
- Participant lost to follow-up
- Death
- *Withdrawal of regorafenib only:*
 - Patients who halt therapy for more than 28 consecutive days - including the 1 week drug holiday. However, continuation of regorafenib may be considered if, in the investigator's opinion, the patient may continue to benefit from the regorafenib treatment, and after consultation with sponsor.
 - Unacceptable toxicity, i.e., event requiring permanent discontinuation of regorafenib according to dose modification guidance in Section 6.6.
- *Withdrawal of nivolumab only:*
 - Patients who experience a delay of more than 10 weeks to receive the subsequent nivolumab infusion due to treatment related toxicity (see exceptions in Section 6.6.2.1)
 - Patients who complete 24 infusions of nivolumab (after approximately 2 years of treatment)
 - Unacceptable toxicity, i.e. event requiring permanent discontinuation of nivolumab according to dose modification guidance in Section 6.6.2.1.

Withdrawal from active FU

Participants *must* be withdrawn from active FU if any of the following occurs:

- At their own request or at the request of their legally acceptable representative. At any time during the study and without giving reasons, a participant may decline to participate further. The participant will not suffer any disadvantage as a result.
- Radiologically confirmed PD is observed and/or clinical progression occurs (provided safety visits have been performed)
- Start of subsequent systemic anti-cancer treatment (provided safety visits have been performed)
- Development of a second primary malignancy that requires a different treatment
- Substantial non-compliance with the requirements of the study
- Withdrawal of consent to active FU visits

- If, in the investigator's opinion, continuation of the active FU visits would be harmful to the participant's well-being
- Participants lost to FU
- Death

Withdrawal from long-term FU

Participants *must* be withdrawn from long-term FU if any of the following occurs:

- Withdrawal of consent to long-term FU
- Participants lost to FU
- Death

Participants **MAY** be withdrawn from the study treatment combination for the following reasons:

- At the specific request of the sponsor and in liaison with the investigator (e.g., obvious non-compliance, safety concerns).
- Withdrawal of nivolumab only: discontinuation of nivolumab may be considered for participants who have attained a confirmed complete response (CR), that have been received at least 8 infusions (32 weeks) of nivolumab and had at least 2 infusions with nivolumab beyond the date when the initial CR was declared.

Discontinuation of study intervention for abnormal liver function should be considered by the Investigator when a participant meets one of the conditions outlined in [Table 6–6](#) or if the Investigator believes that it is in best interest of the participant.

If a clinically significant electrocardiogram (ECG) finding is identified (including, but not limited to changes from baseline in QT interval corrected using Fridericia's formula [QTcF] after enrollment, the Investigator or qualified designee will determine if the participant can continue in the study and if any change in participant management is needed. This review of the ECG printed at the time of collection must be documented. Any new clinically relevant finding should be reported as an AE.

See the SoA for data to be collected at the time of intervention discontinuation and FU and for any further evaluations that need to be completed.

If the participant withdraws consent for disclosure of future information, the sponsor may retain and continue to use any data collected before such a withdrawal of consent. If a participant withdraws from the study, he/she may request destruction of any samples taken and not tested, and the investigator must document this in the site study records.

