- a) Note: The ± 2 d and ± 3 d assessment windows do not apply to collection of PK blood samples.
- b) A mandatory clinical visit to monitor safety will take place 30 d (window of +7 d) after the last administration of regorafenib/nivolumab and 100 d (window of +7 d) after the last dose of nivolumab, with the exception of death or withdrawal of consent.
- c) If tested within 7 days prior to first dose no additional testing on D1 required except for pregnancy testing and abnormal liver function tests.
- d) Contact IxRS to record the following: 1. to register the participant who has signed the PI/ICF (a unique participant identifier will be assigned), 2. the patient is a screening failure (failed to meet the criteria during the screening period), 3. on D1 of every treatment cycle so that the specific participant drug bottle/vial can be provided for dispensing purposes and also in case the participant has discontinued the study treatment (EOT) for any reason.
- e) Tumor genetic alteration(s), as determined by local testing results for MSI status, BRAF, extended RAS
- f) Participant will be followed for treatment related toxicities until these toxicities resolve, return to baseline or are deemed irreversible. All AEs will be documented for a minimum of 100 d after LD of nivolumab or 30 d after LD of regorafenib, whatever occurs later. CTCAE v5.0 will be used.
- g) Serum pregnancy test (for females of childbearing potential only). A negative pregnancy test must be available within 24 hr before study drug administration. Monthly pregnancy testing independent of study drug dosing should be conducted as per local regulations where applicable.
- h) Amylase and GGT will be assessed if clinically indicated.
- i) If protein dipstick result is 3+ or abnormal (based on type of urine test strip used), a laboratory urine analysis should be done for the quantification of proteinuria by urinary protein/creatinine ratio on a random urine sample preferably taken at mid-morning.

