4.1.3 Active Follow-Up

A mandatory clinical visit to monitor safety will take place 30 d (window of +7 d) after the last administration of regorafenib/nivolumab and 100 d (window of +7 d) after the last dose of nivolumab. Longer safety FU for nivolumab is required due to the long half-life of the antibody.

Participants who discontinue study intervention due to radiologically progressive disease will terminate the active FU period after the clinical safety visits.

Participants, who have not progressed clinically or radiologically or have discontinued study intervention for reasons other than death, withdrawal of consent or lost to FU, will continue with radiological tumor assessments. During the active follow-up period, CT (computed tomography) /MRI (magnetic resonance imaging) evaluations will be performed at the same intervals as during study treatment (every 8 weeks for the first year, and thereafter, every 12 weeks). In addition, study intervention-related toxicity/AE and information about survival status and subsequent anti-cancer therapy will be followed up until completion of the active FU.

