10.6 Appendix 6: FU Assessments

Active FU visits

All participants who withdraw from study treatment period for any reason (except death or lost to FU) will be followed for safety at mandatory active FU visits, which will be performed 30 d (+7 d) after the last administration of study treatment regorafenib/nivolumab and 100 d (+7 d) after the last dose of nivolumab.

If the treatment was permanently discontinued after the maximal allowed dose interruption/delay period, 28 d for regorafenib and 6 weeks for nivolumab, the 1st active FU visit should occur within 14 d of the permanent discontinuation. AE assessment and concomitant medication review must be updated at these active follow-up visits and all AEs starting within 30 d after the last dose of study treatment regorafenib (100 d after the last dose nivolumab) should be collected and recorded in the eCRF.

Additionally, for participants who discontinue study treatment without radiological disease progression, drug-related AEs will continue to be collected FU tumor evaluations (by CT or MRI with contrast unless contraindicated) will be performed until radiological progression, occurrence of secondary malignancy and/or start of first subsequent systemic anticancer treatment, whichever comes first, or any other criterion for withdrawal is met.

During the efficacy FU visits, CT/MRI evaluations will be performed at the same intervals as during study treatment (see [Table 1–2](#)). Note: all images still need to be prospectively collected and submitted in DICOM format in case independent central review is needed.

Long-term FU

All participants who withdraw from study treatment period with radiological PD, or from active FU for any reason will be followed for survival and first subsequent anti-cancer treatment, every 3 months (± 14 d) during the long-term FU period, until either data

maturation for the final analysis is reached, or death of the patient, or any other criterion for withdrawal from long-term FU is met. The long-term FU contacts may occur at more frequent intervals at the discretion of the Sponsor. If a patient is lost to FU, the site will try to contact the patient, the patient's relatives, or another doctor treating the patient, unless prohibited by local requirements.

All participants in the long-term FU period will be contacted (telephone contact is sufficient) every month (± 7 d) to determine survival status and obtain information on subsequent systemic anti-cancer treatment.

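### Section 7.1 ends active follow-up for a second primary malignancy without the safety-visit condition, at odds with the mandatory 30-day and 100-day visits

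*Protocol*

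**What the plan says.** In Protocol Section 7.1, under withdrawal from active FU, any one listed event is enough and withdrawal is obligatory. Two bullets are conditional. One is progression. The other reads "Start of subsequent systemic anti-cancer treatment (provided safety visits have been performed", where the bracket closes. The bullet after it, "Development of a second primary malignancy that requires a different treatment", has no condition, and neither does "Substantial non-compliance with the requirements of the study". The separate list in 7.1 of obligatory reasons to stop study treatment also contains "The development of a second primary malignancy that requires a different treatment".

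Three other places govern the safety visits:

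- Section 4.1.3: "A mandatory clinical visit to monitor safety will take place 30 d" after the last regorafenib/nivolumab dose, with a further visit 100 days after the last nivolumab dose. No exception is stated.
- Schedule of Activities (Table 1–2), footnote b: the same two visits, the second described as "100 d (window of +7 d) after the last dose of nivolumab, with the exception of death or withdrawal of consent".
- Appendix 6 (Section 10.6): "All participants who withdraw from study treatment period for any reason (except death or lost to FU) will be followed for safety" at mandatory visits on the same two dates.

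Appendix 6 does mention a second cancer, but as a stopping point for follow-up tumor evaluations: "occurrence of secondary malignancy and/or start of first subsequent systemic anticancer treatment, whichever comes first".

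**The concern.** The same event both stops treatment and triggers withdrawal from active follow-up. A participant who stops both drugs because of a new cancer meets the withdrawal rule while the safety visits still lie ahead. If the new cancer needs systemic therapy, two bullets apply to the same person and disagree: one waits for the visits and the other does not. If it needs only surgery or radiotherapy, the unconditional bullet stands alone.

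What is at stake is the scheduled visit and its laboratory tests. Section 4.1.3 explains the longer nivolumab safety follow-up by the antibody's long half-life. After active follow-up, contact may be by telephone and concerns survival and subsequent therapy (Section 4.1.4, Appendix 6). A call can pick up a reported adverse event. It cannot supply the chemistry and hematology that Table 1–2 schedules at both safety visits.

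**Working it through.** The plan gives no figure to reproduce, so the main check sets the texts side by side.

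**Step 1. Each reason for leaving active FU in 7.1, against the stated exceptions to the safety visits.** Section 4.1.3 states no exception, so it needs no column.

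| Reason in 7.1 | Waits for safety visits? | Exception in footnote b? | Exception in Appendix 6? |
|---|---|---|---|
| Progression | Yes | No | No |
| Subsequent systemic therapy | Yes | No | No |
| Second primary malignancy | No | No | No |
| Substantial non-compliance | No | No | No |
| Visits judged harmful | No | No | No |
| Own request or consent withdrawn | No | Yes (consent) | No |
| Lost to FU | No | No | Yes |
| Death | No | Yes | Yes |

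Three reasons neither wait for the visits nor appear as exceptions. A visit judged harmful is a sensible exception on its merits. For non-compliance, attendance cannot be guaranteed, and Section 7.2 already requires the site to contact the participant and reschedule a missed visit. Second malignancy is the one with no such explanation.

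**Step 2. How many visits are outstanding when the rule applies.** This depends on dosing. The 30-day visit runs from the last regorafenib/nivolumab dose and the 100-day visit from the last nivolumab dose.

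- Both drugs stopped together for the new cancer: both visits are outstanding.
- Nivolumab stopped earlier, regorafenib continued alone (allowed by Sections 4.1.2, 6 and 6.6.1), and the 100-day visit already past: only the 30-day visit is outstanding.
- New cancer found after both visits: none is outstanding.

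**Step 3. What a missed visit would remove.** The duty to document adverse events for the 30/100-day period stays in force (Table 1–2, footnote f; Appendix 6). SAP Section 6.5.5 counts laboratory toxicity as treatment-emergent to 30 days for regorafenib and 100 days for nivolumab, and it only lists unscheduled laboratory data. A replacement test taken off schedule would therefore not enter the laboratory tables. If its result was clinically relevant, it could still reach the adverse-event tables, because Protocol Section 8.2.4 requires such changes to be recorded. What remains exposed is mainly values not judged clinically significant.

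**Step 4. Bound on size.** SAP Section 6.5.2 counts patients rather than events, and n = 70.

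- One affected participant changes a given rate by 0 to 1/70 = 1.43 points; two change it by at most 2/70 = 2.86 points.
- The SAP has 5% reporting cuts (Sections 6.5.2 and 6.5.5). Since 0.05 × 70 = 3.5, four patients are needed. One missed first event could turn 4/70 = 5.71% (shown) into 3/70 = 4.29% (not shown).
- The change is 0 if the site holds the visits anyway, if the participant already had that event on treatment, or if no new event occurs.

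These bounds would apply to any single missing observation. The documents do not say how many participants would be affected.

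**The case against.** The strongest reply is that the conflict appears only if the bullet is read alone. Appendix 6 covers this participant directly: whoever leaves treatment, for any reason but death or loss to follow-up, attends the safety visits. Note b to Figure 1–1 separates the mandatory safety visit from other active follow-up visits. Section 7, and 7.1 itself after its withdrawal lists, refer the reader to the Schedule of Activities for what to collect in follow-up. Section 8 rules out waivers and calls adherence to that schedule essential. On this reading the bullet ends only tumor evaluations.

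As evidence of intent, this stands: the visits are probably meant to happen. It does not settle the wording. None of these texts says which prevails, and the 7.1 bullet is itself a protocol instruction rather than a waiver. Putting the condition on two bullets of one list invites the inference that the others are unconditional.

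A reader might also infer more than the documents support:

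- That both visits are always lost, or that nothing is at risk later than 107 days (100 + 7) after the last nivolumab dose. Neither holds in general, because regorafenib may continue alone and the 30-day visit then runs from its last dose.
- That adverse events cease to be recorded. Footnote f and Appendix 6 keep that duty.
- That second malignancy was left unconditional on purpose. The rationale for the Amendment 2 change is blacked out, so no intent can be read either way.
- That the non-compliance bullet matters equally. Section 7.2 largely covers it.

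**Conclusion.** The point holds as a minor conflict between protocol rules, centred on the second-malignancy bullet. As written, 7.1 requires a withdrawal that three other places do not allow to displace the safety visits. The probable practice is that sites hold the visits.

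The number affected is unknown, likely very small and possibly zero. The 1.43-point bound assumes 70 participants in the safety denominator and one missed first event for each affected participant. Safety analyses are descriptive (SAP Section 6.5), so no test is at risk. The objective response rate is unaffected.

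**What to change.** Either of two small edits to Section 7.1 is enough:

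- Add to the second-malignancy bullet the same safety-visit condition that the progression and subsequent-therapy bullets carry.
- Or, preferably, state once that withdrawal from active follow-up ends tumor assessments but does not waive any outstanding 30-day or 100-day safety visit or adverse-event collection, except for death, withdrawal of consent, loss to follow-up, or visits the investigator judges harmful.

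For substantial non-compliance, do not make withdrawal depend on completed visits. Ask the site to attempt the outstanding visits through the contact-and-reschedule step in Section 7.2, and to document the attempt. The exception lists in footnote b and Appendix 6 could be aligned at the same time.

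The cost is a sentence or two, with no new visits, samples or analyses. The gain for non-compliant participants may be small, since some will not attend.

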7.2 Lost to Follow-up

A participant will be considered lost to FU if he or she repeatedly fails to return for scheduled visits and is unable to be contacted by the study site.

The following actions must be taken if a participant fails to return to the clinic for a required study visit:

- The site must attempt to contact the participant and reschedule the missed visit as soon as possible and counsel the participant on the importance of maintaining the assigned visit schedule and ascertain whether or not the participant wishes to and/or should continue in the study.
- Before a participant is deemed lost to follow up, the Investigator or designee must make every effort to regain contact with the participant (where possible, 3 telephone calls and, if necessary, a certified letter to the participant's last known mailing address or local equivalent methods). These contact attempts should be documented in the participant's medical record.
- Should the participant continue to be unreachable, he/she will be considered lost to FU.

Discontinuation of specific sites or of the study as a whole are handled as part of Section 10.1.

8. Study Assessments and Procedures

- Study procedures and their timing are summarized in the SoA. Protocol waivers or exemptions are not allowed (pre-specified exceptions requiring discussion with the Sponsor are not considered protocol waivers).
- Immediate safety concerns should be discussed with the Sponsor immediately upon occurrence or awareness to determine if the participant should continue or discontinue study intervention.
- Adherence to the study design requirements, including those specified in the SoA, is essential and required for study conduct.
- All screening evaluations must be completed and reviewed to confirm that potential participants meet all eligibility criteria. The Investigator will maintain a screening log to record details of all participants screened and to confirm eligibility or record reasons for screening failure, as applicable.
- Procedures conducted as part of the participant's routine clinical management (e.g., blood count) and obtained before signing of the ICF may be utilized for screening or baseline purposes provided the procedures met the protocol-specified criteria and were performed within the time frame defined in the SoA.

8.1 Efficacy Assessments

Primary endpoint for efficacy assessment is ORR measured by RECIST v1.1 as determined by Radiologist/Investigator. DOR, DCR and PFS will be based on local radiologist/investigator assessment per RECIST v.1.1.

Scans will be prospectively collected and stored at vendor in case independent central review is needed.

All participants who received at least one dose of study drug (regorafenib and nivolumab) will be valid for efficacy evaluations. Contrast-enhanced multi-detector CT is the preferred method to measure lesions selected for response assessment. MRI (typically with gadolinium-based intravenous contrast) may be performed instead of CT (e.g., when local regulations or allergy to CT contrast media do not permit the use of CT as requested per protocol schedule, or when there is concern about radiation exposure from CT, or when MRI is deemed a more appropriate imaging method). Recommended slice thickness for CT/MRI is ≤ 5 mm. PET-CT

scans may be used provided that measurements are obtained from the CT scan and the CT scan is of the same diagnostic quality as a diagnostic CT (with IV and oral contrast). If a CT scan for tumor assessment is performed in a positron-emission-tomography (PET)/CT scanner, the CT acquisition must be consistent with the standard for a diagnostic CT scan (i.e., adequate radiation dose and i.v. contrast) if intended to be used for target lesion measurements. The non-contrast low-dose CT performed as part of the PET scan for attenuation correction is not adequate as a diagnostic CT.

Ultrasound is not useful in assessment of lesion size and should not be used as a method of measurement. Previously irradiated lesions should not be counted as target lesions unless there has been demonstrated progression in the lesion since radiotherapy prior to study enrollment.

For consistency, the same imaging modality and equivalent technique (e.g., slice thickness, field of view) should be used for all scans performed on an individual participant, including baseline scans. At a minimum, anatomical regions that should be included in scans performed at baseline and during study treatment include the chest, abdomen and pelvis, as well as any other areas of known disease and areas prone to metastatic disease for pMMR/MSS CRC.

Tumor assessments will be performed locally by participating radiologists/Investigators and whenever possible all scans taken at each clinical site will be interpreted by the same radiologist/Investigator at that site. Scans must meet the standard of care for imaging of lesions in the respective organ system(s). Unless progression is noted, all lesions will be assessed and reported at each scheduled scan.

All imaging scans (coded with study participant number and in digital imaging and communications in medicine [DICOM] format) as well as imaging-related adjunctive data (e.g., fluorodeoxyglucose [FDG] dose and tracer uptake time) must be prospectively collected and transferred to Bayer, or Bayer-designated imaging core lab, in case independent central review is needed.

The tumor markers CEA and CA 19-9 will be evaluated on an exploratory basis in participants with CRC and will not be used to assess objective tumor response.

Assessment of disease

RECIST v1.1 will be applied by the Investigator as the primary measure for categorization of disease on the baseline imaging and assessment of tumor response until progressive disease (see Section 10.7). CR and PR must be confirmed with repeated imaging performed at least 4 weeks after initial documentation of response.

iRECIST is based on RECIST v1.1, but adapted to account for the unique tumor response seen with immunotherapeutic drugs. iRECIST will be used by the Investigator to assess tumor response and progression, and make treatment decisions (see Section 10.8).

Tumor scans are required at screening, during study treatment and at the End of Treatment: see section 1.3 SoA Table 1–2. Tumor scans are also required during active follow-up, if applicable.

- Baseline assessments will be conducted during the screening period and target lesions should to be selected, measured, and recorded before start of study intervention. Scans that were obtained prior to the participant signing the ICF document for this study can be used as baseline assessments provided that they were performed within 28 d of starting study treatment and meet the requirements for the study

- Assessments during study treatment will be performed every 8 weeks (± 7 d) for the first year and every 12 weeks ± 14 d thereafter. Tumor assessment during the study intervention period includes the same anatomic areas as baseline and will be done until radiological disease progression or the end of the study.
- Radiological tumor evaluation (within 14 days after last study treatment is not necessary if the previous tumor evaluation was performed within 4 weeks (for the first year) or within 8 weeks (thereafter)).
- For participants who discontinue study treatment without disease progression, FU tumor evaluations will be performed until progression of malignancy and/or start of subsequent systemic anti-cancer treatment, whichever comes first, or any other criterion for withdrawal is met. During the active FU period, CT/MRI evaluations will be performed at the same intervals as during study treatment.
- At the Investigator's discretion, tumor scans may be repeated at any time if progressive disease is suspected. For further details, see Sections 10.7 and 10.8.

For participants who show evidence of radiological PD by RECIST v1.1 and are clinically stable, the Investigator will decide whether to continue a participant on study treatment until repeat imaging is obtained using iRECIST for participant management. Participant must be re-consented for continuation of treatment beyond initial documentation of disease progression (If repeat imaging does not confirm PD per iRECIST (iCPD), as assessed by the Investigator, and the participant continues to be clinically stable, study treatment may continue and follow the regular imaging schedule. If PD is confirmed (iCPD), participants will be discontinued from study treatment).

Treatment beyond confirmed progression as per iRECIST is possible if the participant is still benefiting from treatment after documented discussion and approval by the Sponsor.

When clinically stable, participants should **not** be discontinued until progression is confirmed by the Investigator, working with local radiology, according to the rules outlined in Section 10.8. This allowance to continue treatment despite initial radiologic PD takes into account the observation that some participants can have a transient tumor flare in the first few months after the start of immunotherapy, and then experience subsequent disease response. This data will be captured in the clinical database.

For treatment beyond progression as per iRECIST the following needs to be fulfilled:

- Evidence of clinical benefit as assessed by the investigator
- Absence of symptoms and signs indicating unequivocal progression of disease.
- Absence of clinical signs or symptoms of progression despite a rising CEA level.
- No decline in ECOG PS that can be attributed to disease progression
- Absence of tumor progression at critical anatomical sites (e.g., leptomeningeal disease) that cannot be managed by protocol-allowed medical interventions

Participant must be re-consented once for continuation of treatment beyond initial documentation of disease progression. Tumor imaging beyond progression will follow the originally planned intervals and will be conducted using iRECIST.

